## Clinical Investigation Plan

### COMPLIANCE STATEMENT:

This clinical investigation will be conducted in accordance with this Clinical Investigation Plan, the Declaration of Helsinki, applicable Good Clinical Practices and regulations (e.g., US 21 CFR Part 50, 21 CFR Part 56, 21 CFR Part 812 and OUS ISO14155:2020) and the appropriate local legislation(s). The most stringent requirements, guidelines or regulations must always be followed. The conduct of the clinical investigation will be approved by the appropriate Institutional Review Board (IRB)/Ethics Committee (EC) of the respective investigational site and by the applicable regulatory authorities (e.g., FDA, PMDA, MHRA, etc.).

## Clinical Investigation Plan

### 1.0 INTRODUCTION

This registry is a retrospective, observational, non-controlled chart review conducted to support an indication expansion of the Tendril STS 2088 lead to include pacing/sensing in the left bundle branch area.

This clinical investigation will be conducted in accordance with this CIP. All investigators involved in the conduct of the clinical investigation will be qualified by education, training, or experience to perform their tasks and this training will be documented appropriately.

### 1.1 **Background and Rationale**

#### 1.1.1 **Background**

Patients with cardiac disease may exhibit symptoms associated with electrical conduction abnormalities, such as bradycardia (sinus node dysfunction and/or heart block), thereby requiring implantation of a permanent dual-chamber (atrioventricular) or single-chamber (ventricular) pacemaker. However, these pacing modalities are associated with alteration of the normal electrical conduction due to right ventricular (RV) pacing, leading to accelerated progression of left ventricular dysfunction, heart failure, and increasing the risk of heart failure hospitalization and atrial fibrillation. Patients with electrical conduction abnormalities may also present with associated ventricular desynchrony causing further cardiac disease progression into heart failure with impaired left ventricular function.

Physiological pacing achieved by His-bundle pacing (HBP) and left bundle branch area pacing (LBBAP) has emerged as an alternative pacing strategy for patients with pacemaker indications. While HBP can be considered an ideal form of physiological pacing as it activates the heart through the native His-Purkinje conduction system resulting in synchronized contraction of the ventricles obviating RV pacing-related complications, its widespread clinical utility has been limited by technical challenges including lead delivery, accurate His-bundle capture (selective vs. non-selective), and early battery depletion due to high pacing thresholds over time. Left bundle branch area pacing (LBBAP), on the other hand, has been suggested as an effective alternative to overcome the limitations of HBP attributed to the anatomic and histological characteristics of the LBB.

The left bundle branch (LBB) is surrounded by dense myocardial tissue providing a large target zone for pacing owing to its thick, band-like structure. Moreover, the LBB can be activated from the main trunk, the posterior fascicle or the septal fascicle. Therefore, LBBAP presents a lesser technical challenge compared to HBP.

In regard to clinical outcome, it has been reported that LBBAP provides stable and reliable lead parameters at short and intermediate follow-up. The need for a back-up RV lead is deemed unnecessary and device programming is simplified. Furthermore, reported complication rates of the 1343 published cases remain low with LBBAP, and increased threshold at follow-up is infrequent thereby minimizing the need for lead revision. Improvements on clinical outcomes of LBBAP compared to RVP has been further demonstrated by Sharma et al. using results from the Geisinger-Rush Conduction System Pacing Registry with a large multicenter cohort. It has been concluded that LBBAP was associated with a significant reduction in the composite outcome of all-cause mortality, heart failure or upgrade to bi-ventricular pacing.

## Clinical Investigation Plan

### 1.1.2 Rationale for Conducting this Clinical Investigation

LBBAP has emerged as a feasible and safe alternative to traditional pacing modalities with clinical and electrophysiological advantages. This is a retrospective, observational, non-controlled chart review real-world evidence registry to evaluate the safety and effectiveness of LBBA pacing/sensing in patients already implanted with the Tendril STS 2088 lead. The LBBAP data collection registry is designed to support future indication expansion of the existing Tendril STS 2088TC lead to include conduction system pacing in the left bundle branch area (LBBAP). This LBBAP data collection registry is designed in accordance with FDA's guidance documents: Considerations for the Use of Real-World Data and Real-World Evidence To Support Regulatory Decision-Making for Drug and Biological Products – December 2021 and Considerations for the Use of Real-World Evidence to Support Regulatory Decision-Making for Medical Devices – August 2017. Tendril STS 2088TC bradycardia lead is currently market approved under P960013/S46 on May 26, 2009 and CE-marked under CE Cert no. 17 09 01 14607 104 on June 16, 2009, and is indicated for permanent sensing and pacing in either the right atrium or the right ventricle in combination with a compatible pacemaker, implantable cardioverter defibrillator (ICD) or cardiac resynchronization therapy (CRT-P/CRT-D) device.

## 2.0 CLINICAL INVESTIGATION OVERVIEW

### 2.1 Clinical Investigation Objective

The objective of this LBBAP data collection registry is to evaluate the safety and effectiveness of LBBA pacing/sensing in patients already implanted with the Tendril STS 2088 lead.

### 2.2 Device(s) Used in the Clinical Investigation

#### 2.2.1 Name of the Device(s) Under Investigation

Table 1 outlines the devices included in the registry.

**Table 1: Devices Used in the Registry**

Device name	Model/Type	Manufacturer	Region/Country	Investigational or Market Released
Any Abbott market-approved Pacemaker, defibrillator, and/or /CRT device	Any market-approved models	Abbott/St. Jude Medical	All geographies	Market released
Any market-approved pacing, defibrillation, and/or CRT lead(s) – non-LBBAP lead	Any market-approved models	All	All geographies	Market released
Abbott market-approved lead(s) implanted in LBBAP location	Tendril™ STS 2088	Abbott/St. Jude Medical	All geographies	Market released

## Clinical Investigation Plan

Merlin Patient Care System	Any market approved model	Abbott/St. Jude Medical	All geographies	Market released
Delivery catheter and other implant tools	Any market-approved model	All	All geographies	Market released

### 2.2.2 Indication for Use/Intended Purpose

All devices used in this registry are market released. Refer to the specific device IFU for the indications for use.

The Tendril™ STS 2088 leads are indicated for permanent sensing and pacing in either the right atrium or the right ventricle in combination with a compatible device.

### 2.2.3 Description of the Device(s) Under Investigation

Please refer to the country- and device-specific IFU for additional information regarding the devices used in this clinical investigation.

## 3.0 CLINICAL INVESTIGATION DESIGN

This is a retrospective, observational, non-controlled, chart review registry designed to evaluate the safety and effectiveness of LBBA pacing/sensing in patients already implanted with the Tendril STS 2088 lead.

Data from a minimum of 220 attempted subjects will be included in order to have 190 evaluable subjects in this registry. The chart review will be conducted at up to 20 participating centers worldwide.

[figure not shown]
The clinical investigation is a retrospective chart review and therefore involves no pain, discomfort, fear, and any other foreseeable risk as possible for subjects.

### 3.1 Clinical Investigation Procedures and Follow-up Schedule

The flowchart and the follow-up requirements of this clinical investigation are described below.

**Figure 1:** Clinical Investigation Flow Chart

## Clinical Investigation Plan

Data included in this LBBAP data collection registry will be from subjects followed for 6 months ( $\pm$  3 months) after attempted implant of LBBAP location. Data will be collected from previously occurring visits at pre-implant (baseline, required), implant (required), 6 months ( $\pm$ 3 months, required), and 12 months (- 2, +4months, optional).

### 3.2 Measures Taken to Avoid and Minimize Bias and Achieve Systemic Data Collection

To avoid bias, investigators should screen records from every patient with an attempted implant of the Tendril™ STS 2088 lead in the LBBA. Enrollment of consecutive subjects should be attempted.

This registry is designed in accordance with FDA's guidance documents: Considerations for the Use of Real-World Data and Real-World Evidence To Support Regulatory Decision-Making for Drug and Biological Products – December 2021 and Considerations for the Use of Real-World Evidence to Support Regulatory Decision-Making for Medical Devices – August 2017.

The following measures will be taken, but not limited, to ensure that the registry collects both successful and unsuccessful device implantations.

## Clinical Investigation Plan

- Sites should retain an enrollment log which links the subject ID and identifiable information for traceability purposes in order to address inquiries from regulatory agencies, as needed.
- Sites should review patient medical records (i.e., electronic health records) and submit only de-identified data through Case Report Forms (CRFs).
- Sites should make all the effort to collect both successful and unsuccessful LBBAP implantation attempts for the time being applicable to the purpose of this registry by utilizing a device inventory list and/or sales data relevant to the usage of the Tendril™ STS 2088 lead.
- Monitoring by the sponsor will be conducted using a risk-based approach to maintain the reliability and data integrity of the data included in this registry (see details in section 10.6).

### 3.3 Suspension or Early Termination of the Clinical Investigation

While no formal statistical rule for early termination of the clinical investigation for insufficient effectiveness of the device under investigation is defined, the Sponsor reserves the right to discontinue the clinical investigation at any stage or reduce the follow-up period with suitable written notice to the investigator. Possible reason(s) may include, but are not limited to:

- Further product development is cancelled
- Inability to gather adequate patient data

#### 3.3.1 Subject Follow-up for Early Termination or Suspension of Registry

If the Sponsor suspends or prematurely terminates the clinical investigation at an individual site in the interest of safety, the Sponsor will inform all other Principal Investigators.

If suspension or premature termination occurs, the Sponsor will remain responsible for providing resources to fulfill the obligations from the CIP and existing agreements.

The investigator will be requested to return all clinical investigation materials to the Sponsor and provide a written statement to the IRB/EC (if applicable). All applicable clinical investigation documents shall be subject to the same retention policy as detailed in [Section 11.5] of the CIP.

A Principal Investigator, IRB/EC, or regulatory authority may also suspend or prematurely terminate participation in the clinical investigation at the investigational site(s) for which they are responsible. The investigators will follow the requirements specified in the Clinical Trial Agreement.

If a suspended investigation is to be resumed, a prior approval should be obtained from the EC/IRB (if applicable) and a notification should be sent to the regulatory bodies (if applicable).

## 4.0 ENDPOINTS

### 4.1 Primary Safety Endpoint and Rationale

The primary safety endpoint evaluates freedom from LBBAP lead related serious adverse device effects (SADEs) through 6 months post-implant attempt.

## Clinical Investigation Plan

The primary safety endpoint evaluates a LBBAP lead related SADE rate which is an appropriate measure for safety and consistent with the primary safety endpoints used for evaluating performance of the transvenous right ventricular lead. It is appropriate to evaluate the safety through 6 months since it is known that a great majority of complications occur through 3 - 6 months after the implantation.

### 4.2 Primary Effectiveness Endpoint and Rationale

The primary effectiveness endpoint evaluates the composite success rate of acceptable capture thresholds and sense amplitudes for LBBAP at 6 months post-implant. This analysis will be performed with only patients who are successfully implanted with the Tendril™ STS 2088 lead in the LBBA (see details in section 6.1.2). Acceptable ranges for sensing and pacing are shown below:

Parameter	Acceptable values
Pacing voltage	Pacing threshold $\leq$ 2.0V
Sense amplitude	LBBA sense amplitude $\geq$ 5.0 mV or $\geq$ value at implant

The primary effectiveness endpoint evaluates the ability to pace and sense when the Tendril™ STS 2088 lead is implanted in the LBBA. The evaluation of a composite success rate of acceptable pacing thresholds and sense amplitudes is similar to the primary effectiveness endpoints used in for a prior transvenous pacing lead (Tendril FSR 1699T). The 6-month timepoint for assessing the primary effectiveness endpoint is an appropriate time period since these electrical measurements have been demonstrated to be stable starting as early as 1 month post-implant.

### 4.3 Descriptive Endpoints

Descriptive endpoints are reported using only summary statistics and no hypothesis tests will be performed.

- Demographics (if provided): sex at birth, age range
- Indication for pacemaker or CRT-P/D implant
- Cardiovascular (CV) history and other significant medical conditions
- Procedure and device-related adverse events
- Implant success rate for LBBAP lead and reasons for unsuccessful implant
- Number of repositioning attempts at implant
- Overall procedure time: skin-to-skin
- Implant procedure time: vascular access to lead fixation
- Fluoroscopy time and radiation dose
- Implant tools used (i.e., catheter, stylet, etc.): manufacturer, model#
- Capture threshold, pulse width, sense amplitude, and pacing impedance at all follow-up visits
- Mortality
- QRS duration and morphology (if available)
- NYHA classification (if available)
- LVEF, LVEDV, LVESV (if available)

## Clinical Investigation Plan

### 5.0 SUBJECT SELECTION AND WITHDRAWAL

#### 5.1 Subject Population

This clinical investigation will enroll adult male and female subjects over the age of 18 years, who have undergone an attempt of the Tendril™ STS 2088 lead implant in the LBBA and have 6 months of follow-up in their medical records after LBBAP implant attempt.

#### 5.2 Subject Screening and Informed Consent

##### 5.2.1 Subject Recruitment and Screening

Research personnel at each participating center will identify consecutive subjects with an attempt of the Tendril™ STS 2088 lead implant in the LBBA, which comprise the “primary registry” cohort. Subjects are excluded if there is not 6 months ( $\pm$  3 months) of follow-up data available in the medical records after the LBBAP implant attempt.

A member of the site’s clinical investigation team previously trained to the CIP must evaluate patients for the general clinical investigation eligibility criteria, and if applicable, will enter the patients into a site-specific recruitment/screening log. A patient who does not satisfy all general eligibility criteria prior to informed consent (if required) is considered a recruitment failure and should not be enrolled in the clinical investigation.

In case the subject does not meet all inclusion criteria or meets any of the exclusion criteria, the subject is considered a screening failure. The Principal Investigator or the delegated clinical investigation personnel will record the screening failure in the hospital records and on a recruitment/screening log as required.

Each participating site can enroll up to 25 subjects. The sponsor's approval must be obtained to enroll more than 25 subjects in the registry.

##### 5.2.2 Informed Consent

A waiver of Health Insurance Portability and Accountability Act (HIPAA) and a waiver of patient informed consent will be requested at each site’s governing IRB/EC.

The Council for International Organizations of Medical Sciences (CIOMS), in a publication issued jointly with the World Health Organization (WHO), has stated that a waiver of the informed consent requirement may be granted by an Ethics Committee, “when the research design involves no more than minimal risk and a requirement of individual informed consent would make the conduct of the research impracticable (for example, where the research involves only excerpting data from subjects’ records)”. This publication also states that in such research conditions, “medical records and biological specimens taken in the course of clinical care may be used for research without the consent of the patients/subjects”, when approved by Ethics Committee.

This is a retrospective data collection registry that collects only de-identified data. The only risks to patients are related to safeguarding of information. The protocol design includes controls to ensure that there is

## Clinical Investigation Plan

minimal risk to patients. Safeguards include design of the registry to use only de-identified data and reporting pooled results with no direct identification of any individual patient or study center.

It would be impracticable to require individual informed consent from each patient. A requirement of informed consent could introduce sampling bias into the findings of the registry since the subset of patients who would respond to a solicitation for a chart review and who would provide consent might not be representative of the population.

For sites where the governing IRB/EC has not granted a waiver of informed consent, subject will be either informed of the nature of the data collection project by means of the privacy notice, or will be asked to provide a signed written informed consent, as approved by the IRB/EC. The investigators will be responsible to follow the recommended privacy notice or consent rules before starting data collection within this registry.

### 5.2.2.1 Special Circumstances for Informed Consent

The following vulnerable populations are excluded from the registry population:

- Individuals under age of 18 or age of legal consent

## 5.3 Eligibility Criteria

### 5.3.1 General Eligibility Criteria

Assessment for general eligibility criteria is based on medical records of the site. Patients must meet ALL of the inclusion criteria to be considered for the clinical investigation. If ANY of the exclusion criteria are met, the patient is excluded from the clinical investigation and cannot be enrolled (recruitment failure).

### 5.3.2 Inclusion Criteria

#### 5.3.2.1 Inclusion Criteria

- 1) Subject has a de novo attempted implant of the Tendril™ STS 2088 lead in the Left Bundle Branch Area on or before January 31, 2023 and subject's medical records contain data through at least 6 months (+/- 3 months) after LBBAP implant attempt
- 2) Subject is  $\geq$  18 years of age or the legal age, whichever age is greater
- 3) For sites where the governing IRB/EC has not granted a waiver of informed consent, subject has either been informed of the nature of the clinical investigation using a privacy notice or has provided a signed written informed consent, as approved by the IRB/EC (Note: This inclusion criterion is not applicable for sites where the governing IRB/EC or applicable regulation has granted a waiver of patient consent)

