## Clinical Investigation Plan

### 5.4 Subject Enrollment

Subjects are considered enrolled when research personnel at each participating center verify in the health record that all of the inclusion criteria and none of the exclusion criteria are met and, if applicable, local required privacy notice or consent rules have been followed.

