Inclusion Criteria	
 
1) Subject has a de novo attempted implant of the Tendril™ STS 2088 lead in the Left Bundle Branch Area on or before January 31 2023 and Subject's medical records contain data through at least 6 months (<math>\pm</math> 3 months) after LBBAP implant attempt
 
2) Subject is <math>\geq</math> 18 years of age or the legal age, whichever age is greater
 
3) For sites where the governing IRB/EC has not granted a waiver of informed consent, subject has either been informed of the nature of the clinical investigation using a privacy notice or has provided a signed written informed consent, as approved by the IRB/EC (Note: This inclusion criterion is not applicable for sites where the governing IRB/EC or applicable regulation has granted a waiver of patient consent)
 

Exclusion Criteria	
 
1) Subject was enrolled in another clinical trial during this data collection period that might impact the outcomes of the present registry
 

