## 2.3 Endpoint Analysis

### 2.3.1 Primary Safety Endpoint

The primary safety endpoint evaluates freedom from LBBAP lead-related SADEs through 6 months post-implant attempt.

The hypothesis is formally expressed as:

$$\begin{aligned} H_0: & \text{Freedom from LBBAP lead related SADEs} \leq 81.2\% \\ H_1: & \text{Freedom from LBBAP lead related SADEs} > 81.2\% \end{aligned}$$

The primary safety endpoint will be estimated as a binomial proportion and the 97.5% lower confidence bound (LCB) will be calculated using the Clopper-Pearson exact method. The null hypothesis is rejected at the 2.5% significance level if the LCB is greater than the performance goal (PG) of 81.2%. The p-value from a one-sided exact test for the binomial proportion will also be calculated and compared to the 0.025 significance level.

This analysis will be performed on the enrolled population, and the primary safety analysis will use evaluable subjects. Evaluable subjects will include all subjects with an implant attempt with data available for evaluation. Subjects who do not have 6 months data and do not experience a lead-related serious adverse device effect (SADE) prior to 6 months will be excluded from the analysis. Lead-related SADEs that occur through 6 months post attempted implant will be included in the primary safety endpoint analysis. No sensitivity analyses will be performed.

The primary safety endpoint performance goal derivations are provided in Appendix A.

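### Enrolment requires follow-up data in the 6-month (±3) window, so a lead-related SADE followed by death or loss before about month 3 is screened out unseen, and no safety sensitivity analysis is planned

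*Protocol*

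**What the plan says.** **Eligibility.** CIP 5.3.2.1, criterion 1, requires that the "medical records contain data through at least 6 months (+/- 3 months) after LBBAP implant attempt"; Appendix VII repeats it. CIP 5.1 describes the population as patients who "have 6 months of follow-up in their medical records after LBBAP implant attempt". CIP 5.2.1 states the reverse: "Subjects are excluded if there is not 6 months" (±3) of follow-up data in the record. CIP 5.3.1 makes every criterion mandatory, and under CIP 5.4 a subject is enrolled only when site staff "verify in the health record that all of the inclusion criteria and none of the exclusion criteria are met". SAP 2.4.1 also treats data through 6 months as a condition of enrolment, without mentioning the ±3 months. None of these sections makes an exception.

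**Safety analysis.** SAP 2.3.1 analyses evaluable subjects within the enrolled population. It removes "Subjects who do not have 6 months data and do not experience a lead-related serious adverse device effect (SADE) prior to 6 months". By implication, a subject without 6-month data who did have an early lead-related SADE stays in as a failure. SAP 2.3.1 and 2.12 rule out any sensitivity analysis for safety.

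**Screening.** CIP 3.2 asks sites to screen every attempted implant and to use inventory or sales data to find unsuccessful attempts. For a screening failure, CIP 5.2.1 says that the site "will record the screening failure in the hospital records and on a recruitment/screening log as required".

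**The concern.** The safety endpoint runs from the implant attempt, but entry depends on something observed at month 3 or later. A fatal lead-related SADE in the first weeks is the plainest case: the event itself prevents entry, so the SAP rule that would count it is never reached. The schedule of events in CIP 6.2 has a row for death at the implant attempt, and CIP 7.3.1 asks for all deaths. Neither sits well with an entry rule that removes early deaths.

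This is a single-arm comparison with a fixed goal of 81.2%, meant to support an indication expansion. No control arm shares the same selection. If SADE patients drop out of view before the window more often than event-free patients, the observed rate is too favourable, and no planned analysis would reveal it.

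**Working it through.** **Inputs.** Goal 81.2%, one-sided 2.5%, exact binomial (SAP 2.3.1). At least 165 evaluable subjects at 85% power (CIP 8.3.1). At least 220 attempted subjects (CIP 5.6). The assumed SADE rate is redacted, and the documents give no loss rates. Every loss share below is my assumption.

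**The plan's own figure.** At n = 165 the smallest passing count is 144 successes (P(X ≥ 144 | 0.812) = 0.0249). With true freedom of 89.5%, power is P(X ≥ 144 | 165, 0.895) = 0.855, and 165 is the first n to reach 85%. The stated size therefore fits a planning rate near 89.5%. This is a back-solution, not an independent check.

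**Passing count at n = 220.** 191 successes, so at most 29 SADE subjects: P(X ≥ 191 | 0.812) = 0.0173, Clopper-Pearson lower bound 81.6%. With 190 successes the bound is 81.1% and the goal is missed.

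**Effect of selection on a false pass.** Let a share *s* of SADE patients and *r·s* of event-free patients be unenrollable. With true freedom of 0.812,

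p_obs = 0.812(1 − rs) / [0.812(1 − rs) + 0.188(1 − s)], and false pass = P(X ≥ 191 | 220, p_obs).

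For s = 0.10 the SADE term is 0.188 × 0.90 = 0.1692:

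| Event-free loss relative to SADE loss (r) | 0.812(1 − rs) | p_obs | False pass |
|---|---|---|---|
| 0 (extreme) | 0.8120 | 82.8% | 6.2% |
| 0.5 | 0.7714 | 82.0% | 3.5% |
| 1 | 0.7308 | 81.2% | 1.7% |
| 1.5 | 0.6902 | 80.3% | 0.75% |

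Equal loss changes nothing, and heavier event-free loss makes the test harder to pass.

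**How many hidden cases reverse a pass.** First suppose that every screened-out attempt was a failure. Add x failures to 220 subjects and find the smallest x for which the exact p-value exceeds 0.025:

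| Observed SADE subjects | x | Result after adding | p | Lower bound |
|---|---|---|---|---|
| 23 | 9 | 197/229 | 0.034 | 80.8% |
| 26 | 5 | 194/225 | 0.029 | 81.0% |
| 29 | 1 | 191/221 | 0.0252 | 81.19% |

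The count of 23 is the back-solved planning rate (10.5% × 220 = 23.1). If event-free patients are also missing and are added back, more hidden SADEs are needed. From 23 observed with event-free loss at half the SADE rate, it takes 20: s = 20/43 = 0.465, event-free total 197/(1 − 0.2326) ≈ 257, and 257/300 gives p = 0.0254.

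**The case against.** A reader might infer that the two documents contradict each other. They do not. SAP 2.3.1 is written for enrolled subjects and still has work to do for records that end between about month 3 and month 6. Its intention to keep early SADEs is the natural reading, but it is not stated outright.

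A reader might also infer that the safety result is biased upward. The documents do not support that. Serious events under CIP 7.1.2 include hospitalisation and intervention, so SADE patients may be followed more closely than others; that is an assumption, but nothing excludes it. In that case the current rule biases the result downward.

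Nor does the rule remove lead failures in general. A patient with a revision or explant who is still seen in the window remains eligible, and CIP 6.1.3 records those events. An early death without a lead-related SADE would be dropped by SAP 2.3.1 anyway.

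The obvious remedy is to exempt early SADEs from the follow-up requirement. It brings back the failures while early event-free losses stay out. At an assumed true freedom of 89.5% with 10% SADE loss, the bias today and under the exemption would be:

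- r = 0.5: +0.50 points today, −0.49 under the exemption.
- r = 1: 0 today, −1.03 under the exemption.

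On the odds scale the distortion is (1 − rs)/(1 − s) today and (1 − rs) under the exemption. The two are equal in size when (1 − rs)² = 1 − s, which for s = 0.10 gives r = 0.051/0.10 ≈ 0.51. Above about half the SADE loss rate, the exemption is the more biased rule. Where written consent is required (CIP 5.2.2 and criterion 3), patients who died early might still not be enrollable.

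All of these objections stand. They limit the claim and rule out the exemption, but they do not close the gap: the selection exists, and nothing planned would show whether it matters.

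**Conclusion.** The concern holds as a mismatch between the enrolment rule and the natural reading of the safety analysis rule. It affects a narrow group: lead-related SADE followed by death or loss before about month 3. That the group is screened out follows from the text. The size and direction of any bias do not, because they depend on how loss among SADE patients compares with loss among event-free patients, and the documents are silent on that.

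At the assumed 10% SADE loss, the false-pass rate runs from 0.75% to 6.2% across the scenarios shown, against 1.7% with no differential loss. A pass near the critical count is fragile, since one hidden failure reverses it at 29 observed SADEs. At the back-solved planning rate it takes at least nine. Minor to moderate: worth fixing because the check is cheap, not because the primary result is shown to be wrong.

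**What to change.** 1. Keep the eligibility criteria and the exact binomial primary test as they are.
2. Report by site, from the screening logs, how many attempts were screened out for lack of follow-up data in the window. Add vital status and any known lead-related SADE where the log and local consent or waiver rules allow.
3. In SAP 2.3.1 and 2.12, replace the statement that no safety sensitivity analyses will be done with a supportive tipping-point analysis. It adds those attempts back and varies the assumed share with a SADE from none to all, so that it covers loss in both directions.
4. Define what counts as 6-month data in SAP 2.3.1 by reference to the ±3-month window, and reconcile it with the enrolment statement in SAP 2.4.1.

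**Cost.** SAP wording, one more analysis and some extra log reporting. Sites already screen every attempt and log screening failures, but CIP 5.2.1 does not ask the log to hold SADE or vital status, so those details may be incomplete. The sponsor also accepts that a pass close to the critical count may be shown to be fragile.
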